### 8.1.2.2 Building the prior

The CZP prior for this study has been built based on UCB study AS0001.

Study AS0001 was a Phase 3, multicenter, randomized, double-blind, placebo-controlled study to evaluate the efficacy and safety of 2 dose regimens of CZP in subjects with active axial spondyloArthritis (axial SpA). Subjects were randomized in a 1:1:1 ratio to receive one of three treatment regimens:

- CZP administered subcutaneously (sc) at the dose of CZP 400mg every 2 weeks (Q2W) at Weeks 0, 2, and 4 followed by CZP 200mg Q2W sc;
- CZP administered sc at the dose of CZP 400mg Q2W at Weeks 0, 2, and 4 followed by CZP 400mg every 4 weeks (Q4W) sc;
- Placebo.

In this study AS0001, one of the secondary efficacy variables was the change from Baseline in ASDAS; the primary efficacy variable for the current study AS0013.

To build the prior using these data, subjects in the CZP 400mg treatment group were removed since their CZP responses were sufficiently different from those of the CZP 200mg subjects (leaving 105 CZP 200mg subjects with Baseline and Week 12 data available), and the linear model detailed in [Section 8.1.2.1](#) was fitted to just the Placebo and CZP 200mg treatment groups with Placebo as the additive treatment effect (a treatment group by Baseline ASDAS interaction was also included in the model for this historical).

The estimated model was used to estimate the distribution  $\beta_{CZP} \sim N(-1.78, \sigma_{CZP}^2 = 0.0078)$  and might be used as a prior for the CZP mean response. However, in order to take into account expected study to study variation in the estimated CZP parameter  $\beta_{CZP}$ , this prior was discounted (the SD was inflated) to arrive at the prior given in [Section 8.1.2.1](#) (by inflating the SD by 2.788 to give an effective sample size of approximately 20 subjects).

The historical data in study AS0001 gave the opportunity to build an informative prior for the overall effect of Baseline ASDAS in the proposed study (ignoring treatment group since a Baseline by treatment group interaction is not expected). However, since the AS0001 study only included Placebo and CZP treatment group data there is currently no data available with which to confirm whether or not the estimated Baseline ASDAS coefficient of -0.66 for CZP is also similar for BKZ. Accordingly, whilst a Baseline by treatment group interaction in the proposed

study is not expected, to account for this uncertainty a non-informative prior was used for the Baseline ASDAS coefficient.

### **8.1.2.3 Prior data conflict**

Prior data conflict will be investigated for all informative priors through use of graphical displays. If there is evidence of prior data conflict for a given parameter, then a vague prior will be used for that parameter.

### **8.1.3 Presentation of the primary analysis of the primary efficacy variable**

The Bayesian analysis will be implemented using multiple chains each utilizing different starting values for the model specified parameters. The posterior samples from each chain will be combined into one dataset from which the posterior summaries will be estimated. Missing data will be handled as described in [Section 4.2.1](#)

The posterior distributions of the mean changes from Baseline in ASDAS in the CZP and BKZ groups and of the difference in mean changes from Baseline between the treatment groups (CZP – BKZ) will be summarized using means, medians, SDs, 95% credible intervals and 95% highest posterior density intervals. The posterior probability that the difference between treatment groups in the mean change from Baseline in ASDAS at Week 12 is greater than zero will also be presented.

The posterior probability that BKZ achieves a lower ASDAS score at Week 12 compared to CZP will be derived from this distribution.

### **8.1.4 Presentation of Ankylosing Spondylitis Disease Activity Score**

All component data, the derived ASDAS values and changes from Baseline at each visit will be listed by treatment group and subject, including each of the ASDAS disease activity states and disease improvement categories defined in [Section 8.2.1.1](#), based on the FAS. Observed ASDAS values and changes from Baseline will be summarized by treatment group and visit, using descriptive statistics, based on the PPS and repeated for the FAS.

Observed mean values and changes from Baseline, including 95% CI for the means, will be plotted versus time, with both treatment groups overlaid on the same axes, based on the PPS and repeated for the FAS.

### **8.1.5 Presentation of component variables of Ankylosing Spondylitis Disease Activity Score**

All data presentations in this section will be based on the PPS and repeated for the FAS.

#### **8.1.5.1 Bath Ankylosing Spondylitis Disease Activity Index**

The BASDAI score ranges from 0 to 10, with lower scores indicating lower disease activity.

The BASDAI questionnaire contains 6 questions, each of which has a possible value ranging from 0 to 10, and the overall score is calculated as follows:

$$BASDAI = \frac{Q1 + Q2 + Q3 + Q4 + \left( \frac{Q5 + Q6}{2} \right)}{5}$$

To give each symptom equal weighting, the average of the 2 scores relating to morning stiffness (questions 5 and 6) is taken. The sum of the scores from questions 1 to 4 and the average of the scores from questions 5 and 6 result in a total score ranging from 0 to 50. This is divided by 5 to give a final BASDAI score between 0 and 10, with lower scores indicating lower disease activity.

The individual question responses from the BASDAI together with the derived BASDAI score will be listed by treatment group and visit for each subject, including changes from Baseline for the BASDAI score. Additionally, for each subject the mean result from questions 5 and 6, together with the change from Baseline and percentage change from Baseline in this mean value, will be listed.

The observed BASDAI score and changes from Baseline will be summarized by treatment group and visit.

Additionally, the mean of question 5 and 6, together with the corresponding changes from Baseline and percentage changes from Baseline will be summarized by treatment group and visit.

Observed mean BASDAI score and changes from Baseline, including 95% CI for the means, will be plotted versus time, with both treatment groups overlaid on the same axes.

The full BASDAI questionnaire is shown in [Section 14.1](#). A glossary of the BASDAI questionnaire will be presented.

#### **8.1.5.2 Patient's Global Assessment of Disease Activity**

Patient's Global Assessment of Disease Activity will be listed by treatment group, subject and visit, including changes from Baseline and percentage changes from Baseline.

Observed values, changes from Baseline and percentage changes from Baseline will be summarized by treatment group and visit.

Observed mean PGADA and changes from Baseline, including 95% CI for the means, will be plotted versus time, with both treatment groups overlaid on the same axes.

#### **8.1.5.3 High sensitivity C-reactive protein**

Measurements of hs-CRP will be listed by treatment group, subject and visit for each subject including changes from Baseline and ratio to Baseline. The latter will be calculated as follows:

$$\text{Ratio to Baseline} = \text{hs---CRP at Post-Baseline Visit} / \text{hs---CRP at Baseline Visit}$$

Observed values, changes from Baseline and ratio to Baseline will be summarized by treatment group and visit. Summary statistics will include n, arithmetic mean, SD, geometric mean, 95% CI for the means, geoCV, median, Q1, Q3, minimum and maximum.

The geoCV will be calculated as a percentage as:

$$\text{geoCV}(\%) = 100 \times \sqrt{\exp(SD_L^2) - 1},$$

where  $SD_L$  represents the standard deviation of the natural logarithm transformed value.

Observed mean hs-CRP values, changes from Baseline and ratio to Baseline, including 95% CI for the means, will be plotted versus time, with both treatment groups overlaid on the same axes.

The rules for handling any observed concentration values that are BLQ or ALQ are described in [Section 4.2.1.2](#).

## **8.1.6      Supportive analysis of the primary efficacy variable**

### **8.1.6.1      Alternative analysis sets**

The primary efficacy analysis set is the PPS; however, the primary analysis and all supportive analyses of the primary efficacy variable will be repeated using the FAS. These analyses will be performed in order to evaluate the effect that any IPDs may have had on the results of the analysis. The results will be presented as specified in [Section 8.1.3](#).

### **8.1.6.2      Alternative prior distributions**

The primary analysis will be repeated for each of the following prior distribution alternatives:

- A vague prior distribution for all parameters in the model (including the CZP effect).
- An informative prior for the Baseline effect [ $\beta_{bl} \sim N(-0.66, \sigma_{bl}^2 = 25)$ ] and an informative prior for the CZP effect.
- An informative prior for the Baseline effect [ $\beta_{bl} \sim N(-0.66, \sigma_{bl}^2 = 25)$ ] and a vague prior for the CZP effect [ $\beta_{CZP} \sim N(0, \sigma_{CZP}^2 = 10^6)$ ].

The results will be presented as specified in [Section 8.1.3](#).

### **8.1.6.3      Frequentist analysis – Analysis of Covariance**

A frequentist analysis of the change from Baseline in ASDAS at Week 12 will be performed using an analysis of covariance (ANCOVA). The ANCOVA model will match the Bayesian model, ie, including treatment group (CZP and BKZ) as a fixed effect and Baseline ASDAS as a covariate.

Least squares means (LSMeans), SEs and associated 95% CIs for the changes from Baseline in ASDAS at Week 12 in each treatment group will be presented. In addition, the estimated treatment difference in LSMeans (CZP – BKZ), SE, corresponding 95% CI, and p-value for the treatment comparison will be presented.

### **8.1.6.4      Frequentist analysis – Mixed Model Repeated Measures**

A frequentist analysis of the change from Baseline in ASDAS will be performed using a MMRM. This model will use all available change from Baseline in ASDAS data at all post-Baseline visits during the Treatment Period up to and including Week 12. Treatment group (CZP and BKZ), visit, and the treatment group by visit interaction will be included as fixed effects and Baseline ASDAS will be included as a covariate.

An unstructured covariance matrix will be used to model the within-subject errors. If the model fails to converge, and/or if the estimated unstructured covariance matrix is not positive definite, then simpler alternative covariance structures will be considered (eg, compound symmetry).

Least squares means, SEs and associated 95% CIs for the changes from Baseline in ASDAS in each treatment group will be presented by visit. In addition, the estimated treatment difference in LSMeans (BKZ – CZP), SE, corresponding 95% CI, and p-value for the treatment comparison will be presented for each visit. Week 12 will be the primary time point of interest from this analysis.

The LSMeans for the changes from Baseline, including 95% CI, will be plotted versus time, with both treatment groups overlaid on the same axes.

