- Mean, SD, median and CIs will use 1 decimal place more (or 1 more significant figure, depending on the original data reporting format) than the original data
- Coefficient of variation will be reported as a percentage to 1 decimal place

- Minimum and maximum will be reported using the same number of decimal places as the original data
- If no subjects have data at a given time point, then only n=0 will be presented. If n<3, then only n, minimum and maximum will be presented. If n=3, then only n, median, minimum and maximum will be presented. The other descriptive statistics will be left blank.

When reporting individual values and descriptive statistics for PK concentration and hs-CRP data, the following rules will apply with regard to rounding and precision:

- Individual values will be reported to the same level of precision as received from the bioanalytical laboratory
- Descriptive statistics will be reported to the same level of precision as the individual data for the minimum and maximum, to 1 additional significant figure for the mean (arithmetic and geometric), median, Q1, Q3, SD, and to 2 additional significant figures for the 95% CI for the geometric mean
- The geoCV will be reported as a percentage to 1 decimal place

All statistical tests will be carried out 2-tailed at the 5% level of significance unless otherwise stated. The following rules will apply for the presentation of any results relating to inferential statistical analysis:

- P-values will be presented to 4 decimal places; p-values less than 0.0001 will be presented as “<0.0001” and p-values greater than 0.9999 will be presented as “>0.9999”
- Posterior probabilities associated with the Bayesian analyses will be presented as percentages to 1 decimal place
- Means, SDs, medians, 95% credible intervals and highest posterior density intervals obtained from the Bayesian analyses will be presented to 1 decimal place

All statistical output will be presented in statistical appendices where appropriate.

Time to response data (Section 8.3.2.2) will be analyzed for the Treatment Period and across the study (Treatment Period + Treatment Extension Period). All other data tabulations will be performed by treatment group, visit and time point (where applicable) and no separate analyses based on study period will be presented.

The treatment groups will be displayed as follows in the TFLs, where BKZ refers to bimekizumab and CZP refers to certolizumab pegol:

- BKZ
- CZP

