In addition to the primary Bayesian analysis where subjects with missing data will be excluded from the analysis, a supportive analysis based on imputed or predicted values for the change from Baseline in ASDAS at Week 12 will be performed.

Predicted Week 12 values for the subjects who do not have ASDAS values for the Week 12 visit will be obtained from a Mixed Model Repeated Measures (MMRM) analysis. The model will include treatment group, visit and the treatment group by visit interaction as fixed effects (visit as a categorical variable) and Baseline ASDAS as a continuous covariate. Subject-level random intercepts and slopes (visit as a continuous variable) will be included in the model and a 2 x 2

unstructured covariance matrix for these random effects will be used, along with a simple covariance structure for the within-subject errors.

If the model fails to converge then the simpler subject-level model including the intercept as only random effect will be fitted. If there are still problems with convergence and/or if the estimated response covariance matrices (random effects and response) are not positive definite, then alternative models will be considered, eg, allowing the random effects covariance parameters to be unbounded, or modelling the response covariance structure without using random effects.

The combination of observed and predicted values of change from Baseline in ASDAS at Week 12 obtained from the MMRM will then be modelled as the response variable in this supportive Bayesian analysis.

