#### **8.1.6.5 Frequentist analysis – Mixed Model Repeated Measures with Baseline by treatment group interaction**

A frequentist analysis of the change from Baseline in ASDAS will be performed using a MMRM as specified in [Section 8.1.6.4](#). In addition, the model will include the Baseline ASDAS by treatment group interaction.

The results presentation, and the covariance matrix structures, as specified in [Section 8.1.6.4](#), will be applied.

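### The supportive MMRM in SAP 8.1.6.4 has no Baseline-by-visit term, so its Week 12 treatment estimate need not equal the Week 12 ANCOVA even with complete data

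*SAP*

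**What the plan says.** SAP 8.1.6.4 plans a supportive MMRM of change from Baseline in ASDAS, using the post-Baseline visits up to Week 12. Treatment is a fixed effect, and "visit, and the treatment group by visit interaction will be included as fixed effects and Baseline ASDAS will be included as a covariate". On the covariance, "An unstructured covariance matrix will be used to model the within-subject errors", with a simpler structure as fallback. "Week 12 will be the primary time point of interest from this analysis".

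SAP 8.1.6.5 repeats that model with one extra term: "In addition, the model will include the Baseline ASDAS by treatment group interaction".

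SAP 8.1.6.3 plans a frequentist analysis of Week 12 alone. "The ANCOVA model will match the Bayesian model", so it contains treatment and Baseline ASDAS, with the Baseline slope estimated only from Week 12 data.

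SAP 8.1.2.1 describes a separate mixed model that predicts missing Week 12 values for a supportive Bayesian analysis. It carries "Baseline ASDAS as a continuous covariate", together with subject-level random intercepts and slopes and a simple residual structure.

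None of the three repeated-measures models lists a Baseline-by-visit term.

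**The concern.** The response is change from Baseline, so its slope on Baseline ASDAS at a visit is (correlation of Baseline with that visit) × (SD at that visit / SD at Baseline) − 1. If early visits correlate more closely with Baseline than Week 12 does, their slopes are shallower. A single pooled slope then adjusts Week 12 too little for a chance Baseline difference between arms.

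The ANCOVA and the MMRM also use different data: observed Week 12 values in one, all available visits in the other. A reader who sets them side by side may attribute any difference to missing data. With a pooled slope, part of the difference can arise when nothing is missing.

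**Working it through.** **Inputs from the documents.** SAP 2.4 gives a difference of 0.89, SD 1.17, Baseline to Week 12 correlation 0.35, allocation 2:1 and at least 60 subjects at Week 12 (40 bimekizumab, 20 CZP). SAP 8.1.2.2 gives a historical Baseline coefficient of −0.66 for CZP. On the test level, SAP 3.1 says "All statistical tests will be carried out 2-tailed at the 5% level of significance unless otherwise stated". Protocol Table 5–1 schedules hs-CRP, an ASDAS component, at Weeks 4, 8 and 12 of the Treatment Period, so those visits were used.

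**Assumed inputs.** The documents give no Baseline correlation for Week 4 or Week 8. Four patterns were tried, from no decay to strong decay. Between-visit correlations were set at 0.7 (Weeks 4–8 and 8–12) and 0.6 (Weeks 4–12).

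**The plan's own figure.** Residual SD = 1.17 × √(1 − 0.35²) = 1.096. SE = 1.096 × √(1/20 + 1/40) = 0.300. Power = Φ(0.89/0.300 − 1.96) = 84.3% (83.0% with the t distribution). The stated power of at least 80% is reproduced. It is an ANCOVA calculation and does not involve the MMRM.

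**Slope at Week 12.** With equal SDs at Baseline and Week 12 the slope is 0.35 − 1 = −0.65, close to the historical −0.66.

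**The gap.** Let D be the raw arm difference in mean change at Week 12 and d the arm difference in mean Baseline, both bimekizumab − CZP. With complete data:

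- ANCOVA estimate = D − (Week 12 slope) × d
- MMRM estimate as written = D − (pooled slope) × d
- MMRM − ANCOVA = (Week 12 slope − pooled slope) × d

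The SAP presents the ANCOVA contrast as CZP − BKZ and the MMRM contrast as BKZ − CZP. Signs are aligned here.

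The chance difference d has SD 1.17 × √(1/40 + 1/20) = 0.32. If 1.17 is instead the SD of change, the raw SD is 1.17/√(2 × 0.65) = 1.026 and d has SD 0.28.

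**Simulation.** 600 complete trials per row, 40:20, unstructured covariance, REML:

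| Baseline correlation, Weeks 4/8/12 | Raw SD | Mean slope, Week 12 / pooled | Mean gap | SD of gap | 95th percentile of absolute gap | Mean SE, ANCOVA / MMRM as written |
|---|---|---|---|---|---|---|
| 0.35/0.35/0.35 | 1.026 | −0.65 / −0.66 | −0.0004 | 0.017 | 0.034 | 0.263 / 0.262 |
| 0.35/0.35/0.35 | 1.17 | −0.64 / −0.64 | 0.0008 | 0.022 | 0.048 | 0.301 / 0.300 |
| 0.45/0.40/0.35 | 1.026 | −0.66 / −0.60 | −0.0011 | 0.027 | 0.059 | 0.264 / 0.264 |
| 0.45/0.40/0.35 | 1.17 | −0.65 / −0.60 | 0.0006 | 0.027 | 0.056 | 0.300 / 0.300 |
| 0.60/0.45/0.35 | 1.026 | −0.65 / −0.49 | 0.0000 | 0.047 | 0.101 | 0.263 / 0.265 |
| 0.60/0.45/0.35 | 1.17 | −0.64 / −0.48 | −0.0011 | 0.060 | 0.127 | 0.302 / 0.305 |
| 0.75/0.55/0.35 | 1.026 | −0.66 / −0.32 | −0.0058 | 0.095 | 0.199 | 0.265 / 0.281 |
| 0.75/0.55/0.35 | 1.17 | −0.65 / −0.32 | 0.0036 | 0.115 | 0.233 | 0.301 / 0.319 |

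The identity held to about 6e-14 in every trial. A hand check on the last row gives slope difference 0.33 × 0.32 = 0.11, in line with 0.115.

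Across the rows the two estimates agreed to one decimal in 38 to 90% of trials and to two decimals in 4 to 42%.

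**When the gap vanishes.** In one data set forced to equal arm Baseline means, both models gave −1.056 although their slopes were −0.502 and −0.497.

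**With the term added.** The MMRM estimate equalled the ANCOVA estimate in every trial, to within 6e-14, and the mean SEs matched.

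**The case against.** The case for leaving the plan alone is strong on importance. The gap is zero when the arm Baseline means coincide or the two slopes coincide, and it averages about zero over randomisations. Only the most extreme assumed decay brings its SD near 0.1, against an SE of 0.26 to 0.30 and a planned difference of 0.89. If the correlation is constant over visits, the pooled slope is correctly specified. The MMRM is supportive, and Protocol 15.5.2 says that additional analyses do not replace the planned ones. All of this stands, and it limits the point to a small improvement.

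Four stronger readings are tempting, and the documents do not support them:

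- A reader might infer that the MMRM can never agree with the ANCOVA. It can, as the equal-means data set shows.
- A reader might infer that the SAP uses the MMRM as its missing-data check, or requires it to reproduce the ANCOVA. Section 8.1.6.4 states neither aim. The analysis directed at missing Week 12 values is the supportive Bayesian one in 8.1.2.1.
- A reader might treat the prediction model in 8.1.2.1 as the same model. It has random effects and a different residual structure, and it fills in only missing Week 12 values. No magnitude was computed for it.
- A reader might expect the added term to make 8.1.6.5 match the ANCOVA. It would not, because 8.1.6.5 includes Baseline-by-treatment and the ANCOVA does not.

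What the objection leaves standing is that the gap is avoidable and unrelated to missing data.

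**Conclusion.** The point holds for SAP 8.1.6.4, in the form that its Week 12 estimate need not equal the Week 12 ANCOVA with complete data. The algebra is exact; the size depends on assumed Week 4 and Week 8 correlations. The SD of the gap is about 0.02 with no decay, 0.03 to 0.06 with moderate decay and about 0.1 with strong decay. It is extra noise and incomplete adjustment for chance imbalance, with no systematic bias in the treatment effect.

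A reader might infer that the trial's conclusion is at risk, but it is not. The primary Bayesian regression uses a single visit and so already has a Week 12 slope. The Proof of Concept criterion and the stated power are likewise unaffected.

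**What to change.** In SAP 8.1.6.4, add a Baseline ASDAS-by-visit interaction to the fixed effects. With complete data and the unstructured covariance, the MMRM then reproduces the Week 12 ANCOVA and adjusts Week 12 with its own slope. No claim is made for the fallback covariance structures.

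For consistency the same term can be carried into 8.1.6.5 and into the prediction model in 8.1.2.1, without expecting agreement with the ANCOVA there.

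The cost is one model term and a few degrees of freedom: with three visits, two extra slope parameters. Where the slopes really are equal, the simulated mean SE rose by only 0.001 (0.262 to 0.263, and 0.300 to 0.301). Under the strongest assumed decay it fell from 0.281 to 0.265 and from 0.319 to 0.301.
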